Trial Study Design Overview: This is an open-label, multi-site, randomized controlled trial aimed at assessing a simplified initial treatment approach (fixed-, moderate-dose combination) of statin and/or ARB, in this case simvastatin 20 mg once per day, and/or losartan 25mg once per day; for reducing cardiovascular risks among SMI patients who have received standing 2GA therapy anytime within 6 months prior to study enrollment. These patients are at elevated cardiovascular risk but frequently do not receive recommended monitoring or treatment. We hypothesize that this monitoring/treatment failure reflects both the fragmentation of care delivery for these patients and low patient adherence; accordingly, our trial assesses a simplified treatment initiation strategy that uses a moderate-dose, fixed drug regimen, which has been tested successfully in other patient populations and in other parts of the world. We have two study arms: 1) Intervention consisting of treatment initiation with a fixed-dose regimen of a statin and/or an ARB; and 2) Usual treatment; We will also follow non-Randomized subjects who signed consent, but were not eligible to continue on to randomization into the Intervention or Usual Treatment arms. Table 1 displays the six assessment steps. Assessment steps will be the same for each study site.

The efficacy of statins to reduce cholesterol levels and for ARBs to reduce blood pressure is not in doubt. In this study, we are assessing whether our study design enables a high degree of adherence with these medications. As described below, we will prescribe a statin and/or an ARB to eligible patients, including subjects in the study who are already on one of the two study medications and prescribe the one they are not on. In the latter case, we will use adherence with the new medication as the outcome.

Although we have designed this study to ensure the lowest possible adverse event profile by providing a fixed low dose of each medication, some patients nonetheless complain of side effects and some randomized to the intervention arm have decided to

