receiving treatment for increased cardiovascular risk (i.e. subjects who are already prescribed either a statin or ARB drug). In this case, subjects will be given the remaining non-prescribed medication (e.g. subjects already receiving treatment with a statin will be prescribed losartan, and subjects receiving any anti-hypertensive treatment will be prescribed simvastatin). We will not alter the dosing of any previously prescribed medication, including any statin or anti-hypertensive medications. Subjects who are already receiving both medications, will be included in the non-randomized group. We will include patients with state appointed legal guardians or health proxies with durable power of attorney who have the specific authority to make mental health care decisions or to consent to participate in research. Guardians or proxies will use substituted judgment when deciding to enroll the patient in this research study. State sponsored legal guardians are the preferred surrogate, however, we will accept health care proxies with durable power of attorney; no other form of surrogate will be accepted, participants with other forms of surrogates that are unable to provide consent on their own will be excluded. The relationship between the participant and surrogate will be recorded on the informed consent form that all parties have signed. We will include patients who cannot speak English. We will follow the PHRC policy on Obtaining and Documenting Informed Consent of Subjects who do not Speak English as found on the PHRC website at http://navigator.partners.org/ClinicalResearch/Non-English Speaking Subjects.pdf. An attempt to administer all aspects of the proposed research will be made through the use of an official translating service (i.e. electronic, phone, or in person translator). The consenting process for non-English speakers will always be done in the presence of an official hospital translator when using the short from consent procedure. Any measures that are invalidated by translation will be discarded during analysis. Since our primary measures are adherence, evidence through pill counts and improvement in metabolic risk factors, there is still value to the study and the subject to participation of non-English speakers.

Other inclusion criteria include the following:

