- Incident or prevalent cases of SMI: including schizophrenia, schizoaffective disorder, bipolar disorder, major depressive disorder, and psychosis NOS with some evidence of functional impairment.
- Age 18 years and older.
- Recent treatment with a 2GA, e.g., having received treatment with a standing 2GA anytime in the past 6 months. Concomitant psychotropic medications will be allowed as there are no contraindications with this regimen. Ongoing treatment of their mental illnesses at one of three mental health clinics: McLean Hospital (McLean outpatient clinicians), BayCove, Edinburg Center, and Mass Mental Health Center, defined as entering one of the treatment programs as a de novo patient (new disease) or having been diagnosed >2 years ago and had at least six visits in the past 12 months (prevalent disease).

The exclusion criteria are as follows:

Unstable/active disease or potential contraindications, e.g., diabetes, unstable
angina or recent acute coronary syndrome, pregnancy, very high risk factors on
the screening labs (e.g., CPK>2*ULN, liver disease (AST> 2*ULN ALT> 2*ULN)

; A1c>7%;), renal failure (creatinine ≥1.3mg/dL or GFR<60 mL/min/1.73m²), liver failure, or both statin and angiotension drug contraindications (when possible we will provide the study medication that does not interact with previously prescribed medications, i.e. subjects taking lithium will only be prescribed simvastatin since anti-hypertensives are contraindicated with lithium). Participants whose screening labs indicate high cholesterol (LDL > 200 mg/dL), hypertension (SPB > 160 mmHg), or hypotension (SBP< 120 mmHg) will be included; however we will not prescribe both study medications; we will only provide the study medication that can be taken safely. For example, a participant with high cholesterol will be referred to their PCP for care and administration of a statin, but could still receive losartan in the treatment arm.

- Unable to provide informed consent, e.g., has dementia, developmental disability, other cognitive disorder, or fails screening mini-mental status exam.
- Women who are pregnant or breastfeeding

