Characterization of Usual Treatment: We also will carefully describe care under Usual Treatment, including the timing of initiation, treatment choice, adherence, prescribing clinicians, and visit patterns for subjects in the control arm. We will characterize the involvement of other clinicians for subjects in both arms, and clinic traits.

Treatment Operational Definition: To start, we will use the same treatment definition for both study arms, i.e., current use of a statin and angiotensin drug. Because there are multiple potential drugs for cardiovascular prevention, we will alter this definition in a series of sensitivity analyses. For example, we will examine a minimal cardiovascular treatment variable in which we define treatment as current use of any cardiovascular drug, independent of the therapeutic class or mechanism of action. We also will examine a partial treatment variable in which we count the number of distinct cardiovascular prevention drugs.

Analysis approach 1: We will plot the percent on "adequate" CVD prevention care, at baseline and the four quarterly follow up times to monitor how treatment activity unfolds over time in the two arms of the trial. At any given follow-up point we will be comparing

two binary outcomes (on or off treatment) and will use standard methods for comparing two proportions to test statistical significance and get confidence intervals for the difference in the percent on treatment in the two arms. We will use a Bonferroni correction so the four separate tests or CIs will have an overall level of 0.05 or 95% CI, respectively.

Analysis approach 2: We will use all available follow-up data to construct a summary measure of the mean percentage of follow-up time during which each group was on treatment. Since we expect the distribution of outcomes to be non-normally distributed, we will get a test of significance for no difference between the mean outcomes in the two arms using a randomization test. A 95% confidence interval for the difference of percentage of time on Tx will be obtained using bootstrap methods. We will use STATA 13.0 for all analyses.

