Primary study outcome: The main outcome is use of the cardiovascular prevention medications over the 12-months after study initiation. For each individual, we define the primary outcome as the proportion of the 12 follow-up months during which she/he either received any of the prescribed medication or the medication became clinically contraindicated after trial entry (as decided by the treating physician). We will assess the outcome using medication counts at each study visit (i.e., at the 3-, 6-, 9-, and 12-month study visit), supplemented by subject self-reports and the clinic chart review. For subjects who are eligible to receive both statins and ARB medications at baseline, we will calculate the number of days that they receive both medications during the 12 months of follow-up. For subjects who are eligible to receive only one of the two medications at baseline (i.e., because of pre-existing therapy with or because of contraindications to the other prevention medication before trial entry), we will calculate the number of days that they receive the medication during the 12 months of follow-up, with the same approach for addressing changes in subsequent eligibility.

Analysis of the primary study outcome: The primary analysis will follow the intention-to-treat (ITT) principle. We will use regression analysis to estimate the mean average of the primary outcome in each group and the difference between the mean outcomes, along with its 95% confidence interval and using the p-value for a null hypothesis. If clinically meaningful imbalances are detected in baseline covariates despite randomization, we will adjust for those covariates. If necessary, we will adjust for selection bias due to loss to follow-up via inverse-probability weighting. In supplemental analyses to the main ITT approach, we also will conduct appropriately adjusted per-protocol analyses. We will use STATA 13.0 for all analyses. We also will examine a number of pre-specified subgroup analyses, in which we examine whether the intervention might be more effective among those SMI patients who are more likely to receive fragmented care or less likely to be adherent to complex treatment regimens, e.g., SMI patients with Medicaid versus those with commercial health insurance.

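### The protocol's main Aim 1 definition requires a statin and an angiotensin drug, but the protocol gives some intervention participants only one; the SAP repairs this only in part

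*Protocol*

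**What the plan says.** **The outcome definition.** Protocol section VI, Treatment Operational Definition: "we will use the same treatment definition for both study arms, i.e., current use of a statin and angiotensin drug". Looser versions come second: "we will alter this definition in a series of sensitivity analyses". Two are named, use of any cardiovascular drug and a count of distinct prevention drugs. Analysis approach 1 compares the percentage on treatment at each of four quarterly visits, with a Bonferroni correction.

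**The prescribing rules.** Protocol section III, and Table 1 Step 3, give one study drug only to several groups:
- Prior blood-pressure treatment of any class: "subjects receiving any anti-hypertensive treatment will be prescribed simvastatin".
- Lithium: "subjects taking lithium will only be prescribed simvastatin since anti-hypertensives are contraindicated with lithium".
- Screening values: "Participants whose screening labs indicate high cholesterol (LDL > 200 mg/dL), hypertension (SPB > 160 mmHg), or hypotension (SBP< 120 mmHg) will be included", with the rule that "we will not prescribe both study medications; we will only provide the study medication that can be taken safely".

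**Other statements in the protocol.** The Trial Study Design Overview says of participants already on one study medication: "In the latter case, we will use adherence with the new medication as the outcome". The Aim 1 analysis text and the Power Calculations both take every intervention participant to begin on treatment.

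**The SAP.** Under Primary study outcome, participants eligible for one drug at baseline are scored on that drug alone. The reasons listed are "because of pre-existing therapy with or because of contraindications to the other prevention medication before trial entry". Time after a drug becomes contraindicated is credited. Participants eligible for both drugs are scored on days with both, although the general definition in the same paragraph counts time on any one of the prescribed drugs.

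**The concern.** The prescribing rules and the outcome rule do not match. At entry, an anti-hypertensive of any class means that losartan is not prescribed. At follow-up, only an angiotensin drug satisfies the definition. A participant on lithium, or on an anti-hypertensive from another class, can take every simvastatin tablet dispensed and still be recorded as off treatment at all four visits.

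Aim 1 asks whether the strategy raises use of preventive treatment. Counting adherent participants as failures makes the strategy look weaker than it is. The protocol and SAP also hold three different rules for one-drug participants (Overview, Aim 1 definition, SAP). Unless one is fixed in advance, the choice could be made after results are known.

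**Working it through.** **1. Who is affected under the Aim 1 definition.**

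| Intervention participant, fully adherent | Study drug given | Meets the two-drug definition? |
|---|---|---|
| Eligible for both | both | yes |
| Keeps own statin | losartan | yes |
| Keeps own angiotensin drug | simvastatin | yes |
| Own anti-hypertensive of another class | simvastatin | no, unless an angiotensin drug is added elsewhere |
| Lithium | simvastatin | no, same condition |
| LDL > 200 | losartan possible; referred to PCP for a statin | only if the PCP starts the statin |
| SBP > 160 or < 120 | one drug only | only if the other class comes from elsewhere |

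Rows two and three are not misclassified. The problem lies in the last four.

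**2. What the SAP covers.** Lithium (described in the protocol as a contraindication), other contraindications, and prior statin or angiotensin use fall in its single-drug group. Users of another anti-hypertensive class, and participants referred out for LDL > 200 or SBP > 160, are not clearly in either group. The SAP neither restates nor withdraws the four visit-level tests.

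**3. The plan's own figure.** Power Calculations: 150 per arm, control use 15% (stated as below 15%), one-sided alpha 0.0125; stated power 80% for 26 points and 90% for 20 points. A pooled-variance two-proportion calculation gives 99.8% and 96.5%, so the stated pair does not reproduce. The larger difference also carries the lower stated power, which cannot be right. That is a separate matter; it matters here because the calculation assumes nobody is barred from the definition.

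**4. Size of the dilution.** Let f be the share who are prescribed one drug and lack the other class. The documents do not give f. Assume 70% of intervention participants use what they are prescribed and 15% of controls are on treatment, a difference of 70 − 15 = 55 points.
- Both arms scale: difference = (0.70 − 0.15)(1 − f). This is natural for groups defined at baseline and then randomised.
- Adverse case, control unchanged: difference = 0.70(1 − f) − 0.15.

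| f | Intervention | Difference, both scale | Difference, control 15% |
|---|---|---|---|
| 10% | 63% | 49.5 | 48 |
| 20% | 56% | 44 | 41 |
| 30% | 49% | 38.5 | 34 |
| 40% | 42% | 33 | 27 |

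**5. Effect on power.** Even the last adverse cell, 42% versus 15%, keeps about 99.9% power. If the true difference is the protocol's smaller value of 20 points (35% versus 15%), the loss is larger:

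| f | Power, both scale | Power, control 15% |
|---|---|---|
| 0 | 96.5% | 96.5% |
| 20% | 89.4% | 69.3% |
| 40% | 75.1% | 18.6% |

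**The case against.** The strongest reply is that the later SAP settles the matter. The protocol offers its definition as a starting point, its Aim 2 text promises to finalise the analysis before outcome data are examined, and the SAP then names a tailored primary outcome. This stands for contraindications and for prior statin or angiotensin use. A reader might infer that every one-drug participant also scores zero under the SAP. The text does not support that. Users of other anti-hypertensive classes can be read into the single-drug group, because the protocol gives them only simvastatin, and the sentence crediting any one prescribed drug would count them. The SAP is ambiguous here; it does not fix a zero score.

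Three further replies have weight:
- The drug-count sensitivity analysis credits one added drug, so the protocol is not blind to partial treatment. It is still secondary to the two-drug rule. The any-drug version is met at baseline, in both arms, by everyone already on partial therapy.
- Two-drug coverage under a common rule is a legitimate strategy outcome, and dilution is conservative for superiority. But the Overview and the SAP both say that one-drug participants should be judged on that drug, so the two-drug rule departs from the plan's own intention.
- Counting any anti-hypertensive class at follow-up would move the target away from the SAP's statin and angiotensin classes. That is a trade-off, not a correction, and is not asked for here.

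**Conclusion.** The protocol's Aim 1 definition conflicts with its one-drug prescribing rules, with its Overview, and with its premise that all intervention participants start on treatment. Applied as written to the visit-level tests, it is a wrong rule and not just a missing detail. For the SAP primary outcome, the defect is limited to unclear placement of some groups and to the clash between any one drug and both drugs.

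The main effect is understatement of the arm difference: from 55 points to between 49.5 and 33 if both arms scale, or to between 48 and 27 in the adverse case, for f from 10% to 40%. These are scenarios resting on assumed 70% and 15% use and an unknown f. The f range includes groups that the SAP already handles, so it describes the visit-level tests and not the residual SAP gap. A reader might infer that the trial's conclusion is at risk. That does not follow under the 70% assumption, where power stays near 99.9% or above; it becomes a real possibility only if the true difference is nearer 20 points and f is sizeable.

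**What to change.** Reconcile the Overview, the Aim 1 text and definition, and the SAP primary outcome into one rule:
1. From baseline data, in both arms, derive the set of study drug classes (statin, angiotensin drug, or both) that each participant would be prescribed under the protocol's existing rules.
2. Score both the four visit-level outcomes and the proportion-of-time outcome against that set.
3. State in the SAP that the single-drug group includes everyone the protocol gives only one drug, naming users of any anti-hypertensive and the LDL and SBP groups.
4. Choose between any prescribed drug and both drugs for participants eligible for both, and delete the other wording.
5. In the any-cardiovascular-drug sensitivity analysis, count only drugs not taken at baseline.
6. Correct the statement that all intervention participants start on treatment so that it refers to their assigned set.

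One case must be reconciled first. For a participant on both a statin and a non-angiotensin anti-hypertensive, the two examples in section III point to different study drugs, so no set can be derived until the protocol says which applies.

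The cost is wording in two documents and one derived baseline variable. Medication lists, LDL and SBP are already collected. The target will differ between participants, so results should also be shown by set. No prescribing rule changes.

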Study nurse prescribes fixed dose statin and/or ARB drugs (Intervention arm only). If subjects are randomized into the treatment arm and are already taking either a statin or any anti-hypertensive medication, they will be prescribed only the drug they are not already taking (e.g. participants on a statin will be prescribed only losartan). If subjects are already taking either a statin or anti-hypertensive medication, we will not alter the dosage of the previously prescribed medication.

We will send letters about the trial to the subject's PCP, regardless of subject's randomization.

Intervention arm subjects will get an additional blood draw in-between the medication visit and first follow-up visit to ensure it is safe for them to continue taking the study medications.

Step 4: Follow-up Visits (every 3 months for 12 months)

RAs conduct follow-up interviews, perform pill counts, and collect urine pregnancy tests (all arms)

Study nurses collect blood samples and vital signs; conduct safety checks; track visits (dates, clinician type), diagnoses, prescription drugs (names, doses, pill counts of cardiovascular drugs), and medical events (all arms)

Study nurses will record and reconcile medication lists at every visit, and note changes in medications.

Study nurse prescribes additional fixed dose statin and/or ARB drugs (Intervention arm only).

Participants who have baseline CK values within 2*ULN will be enrolled in the study. If these participants are randomized into the treatment arm, and will be receiving treatment with a statin, they will be asked to come for additional safety blood draws once per month in addition to one draw one week following the first dose of study drugs. This draws will be done to ensure participant safety while taking the study medications. If a trend of increasing CK is observed, the study medications will be discontinued (Intervention arm only).

Participants prescribed the ARB who exhibit symptoms of hypotension (e.g., syncope, dizziness) and/or have an SBP measurement of <100 mmHg at the follow-up visit will additionally be evaluated for orthostatic hypotension and tachycardia. Study PIs will be notified, and will make a decision based on these criteria to either continue or discontinue the ARB at this time. These participants will be asked to come back within one week of their follow-up visit for an additional blood pressure check. (Intervention arm only).

Step 5: Final Assessment

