**NCT02188121**

Protocol Title: Clinical trial to reduce cardiovascular health risks in  
patients with serious mental illness

Statistical Analysis Plan Date: 02/10/2018

Background: This trial focuses on SMI patients who are potentially eligible for cardiovascular prevention therapy (through statin and angiotensin medications such as angiotensin receptor blockers or ARBs) but who have not yet received it. The trial compares a prevention strategy intervention with usual care with respect to use of therapy. The trial includes those on partial therapy and excludes those with detected cardiovascular disease or diabetes, and assesses whether the intervention increases cardiovascular prevention use relative to usual care.

Eligibility summary: Eligibility criteria include a diagnosis of schizophrenia, schizoaffective disorder, or bipolar disorder; second generation antipsychotic (2GA) therapy within the past six months before trial entry; and mental health care at one of the study sites at the time of trial entry. We exclude subjects who already have a diagnosis of diabetes or cardiovascular disease; who already are receiving therapy with both statins and angiotensin medications (i.e., the same therapeutic drug classes as used in the intervention); or who have contraindications to both drug classes.

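### The Aim 1 any-cardiovascular-drug sensitivity definition counts therapy already in use at randomisation, which attenuates the between-arm difference by an unstated amount

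*Protocol*

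**What the plan says.** **Who is randomised.** Protocol section III (Eligibility) includes "subjects who are already prescribed either a statin or ARB drug", and the protocol's Table 1, Step 3, widens the second class to any antihypertensive. The SAP Background agrees: "The trial includes those on partial therapy". People already on both classes go to the non-randomised group. In the intervention arm, those on one class keep it at its existing dose and "they will be prescribed only the drug they are not already taking".

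**How they are scored elsewhere.** For participants given only the missing drug, the Trial Study Design Overview states: "In the latter case, we will use adherence with the new medication as the outcome". The SAP's primary outcome is consistent with this. It has a separate rule that begins "For subjects who are eligible to receive only one of the two medications at baseline", names pre-existing therapy as one reason, and counts days on that one drug.

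**How Aim 1 scores them.** Under Treatment Operational Definition (protocol section VI), the starting definition in both arms is "current use of a statin and angiotensin drug". Two alternatives follow as sensitivity analyses. The minimal one will "define treatment as current use of any cardiovascular drug, independent of the therapeutic class or mechanism of action". In the partial one, "we count the number of distinct cardiovascular prevention drugs". Neither mentions drugs already in use at baseline. The SAP neither repeats nor withdraws these two definitions.

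**The concern.** Take a participant who enters on a statin and stays on it. Under the any-drug definition that person is on treatment at baseline and at all four quarterly visits, in either arm, whether or not losartan is offered or taken. The value cannot respond to the intervention. The larger this group, the higher both arms' rates and the smaller the gap between them.

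What is at stake is interpretation. If the any-drug difference comes out clearly smaller than the difference under the starting definition, a reader may conclude that the result is fragile to how treatment is defined. The shrinkage could instead come only from how many people were partly treated at entry, and an analysis reported only for the whole sample cannot tell the two apart.

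**Working it through.** **Inputs from the protocol (Power Calculations):** 150 per arm; one-sided alpha 0.0125 (z = 2.241); control rate below 15%, taken as 15%; a 20-point difference, so 15% versus 35%.

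**Assumptions, because the documents give no figures:**
- f is the share of randomised participants on one class at entry, varied from 0.2 to 0.4.
- s is the fraction of them still on that drug at the visit, equal in both arms and independent of uptake of the new drug.
- The 15% and 35% are rates of new-drug use, the same whether or not someone is partly treated at entry.

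**Power formula** (two proportions, pooled variance under the null), with m the mean of the two rates:

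power = Φ{ [(p₂ − p₁)√n − z√(2m(1 − m))] / √(p₁(1 − p₁) + p₂(1 − p₂)) }

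**The plan's own figures first.** For 15% versus 35%: (0.20 × 12.247 − 2.241 × 0.6124) / 0.5958 = 1.81, so power is 96.5%. For 15% versus 41% it is 99.8%. The protocol states 90% for 20 points and 80% for 26 points. Those figures do not reproduce, and they give less power to the larger difference. That is a separate matter; only the inputs are used here.

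**Any-drug rates.** A person untreated at entry is on a drug with probability p. A person on prior therapy is on some drug with probability s + (1 − s)p. Averaging over the two groups:

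rate = f·s + (1 − f·s)p, so difference = (1 − f·s)(p₂ − p₁)

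| f | s | Control | Intervention | Difference | Power |
|---|---|---|---|---|---|
| 0 | – | 15% | 35% | 20 points | 96.5% |
| 0.2 | 1 | 32% | 48% | 16 points | 72% |
| 0.3 | 1 | 40.5% | 54.5% | 14 points | 57% |
| 0.4 | 1 | 49% | 61% | 12 points | 44% |
| 0.3 | 0.7 | 32.9% | 48.7% | 15.8 points | 71% |

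With s = 1, power falls below 80% at about f = 0.15. For a 26-point effect it does so at about f = 0.32, with 92% power at f = 0.2 and 69% at f = 0.4.

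**Splitting by baseline therapy.** Among those untreated at entry the difference is the full 20 points. If the strata split evenly between arms, f of 0.2, 0.3 or 0.4 leaves 120, 105 or 90 untreated per arm. The same formula gives power of 92%, 87% or 81% in that stratum alone, more than the diluted whole-sample comparison at s = 1.

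**Drug count.** Assume untreated people add two drugs or none, and partly treated people keep one and may add one. The mean difference is (1 − f) × 2 × 0.20 + f × 0.20 = 0.40 − 0.20f: 0.40 at f = 0, 0.32 at f = 0.4 and 0.20 at f = 1. The prior drug appears in both arms and cancels. The decline with f arises because partly treated people have only one drug left to add; change from baseline would show the same decline. Power under this model stays between 86% and 97%.

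**The case against.** The strongest reply is that the variable does what it is meant to do. The protocol sets out deliberately to vary the definition because several drugs prevent cardiovascular disease. Whether a person is on any such drug is a legitimate coverage question, and crediting other drugs is its purpose. The new-medication rule belongs to a different outcome, so departing from it in a sensitivity analysis is not in itself an error. This stands, and it is why the variable should be kept. It does not remove the need to show how much of a smaller difference comes from prior therapy.

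The arithmetic at s = 1 is also the unfavourable end. The protocol itself expects poor adherence to chronic drugs and counts people lost to follow-up as not on care, so s will be below 1 and the attenuation smaller. This stands too.

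Three stronger readings are tempting, and the documents do not support them:
- *The analysis cannot show an effect.* Participants untreated at entry still carry it; the difference vanishes only if everyone is partly treated and all stay on the prior drug.
- *The drug count is biased toward zero in the same way.* A count classifies nobody as treated, and randomisation balances prior drugs between arms in expectation. They add variance only.
- *The definition breaks the premise, in Aim 1 and Power Calculations, that controls start off treatment.* That premise is coherent under the starting definition, which requires both classes, because people on both are not randomised. The protocol does not apply it to the sensitivity variables and claims no power for them.

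**Conclusion.** The point holds for one sensitivity definition. As written, the any-drug analysis mixes the effect of the intervention with prescribing that predates randomisation, and its risk difference is attenuated by about 1 − f·s. For a 20-point effect that means a loss of 4 to 8 points at f of 0.2 to 0.4 with full persistence, and less with lower persistence. The size rests on assumed values of f and s, on persistence being equal between arms and independent of new-drug use, and on equal uptake in both baseline groups. The direction follows whenever some partly treated participants stay on their prior drug, given similar persistence in the two arms.

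The SAP primary outcome is not affected, since it already scores one-drug-eligible participants on that drug. This is an inexpensive improvement to secondary analyses, not a threat to the trial's main conclusion.

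**What to change.** 1. Keep the any-drug variable, but report its between-arm difference by baseline cardiovascular therapy (none versus partial) beside the overall figure. Alternatively, add next to it a version that counts only classes absent from the reconciled baseline medication list.
2. For the drug count, adjust for the baseline count or analyse change from baseline.
3. State the share on partial therapy at entry, by arm, so that readers can judge the dilution.

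No new data are needed: the protocol already has medications recorded and reconciled. The wording can go in when the analytic protocol is finalised, which the protocol places before outcome data are examined. The cost is slightly more analysis and smaller strata. A new-class-only version also has a blind spot: it does not register someone stopping a baseline drug, so it should accompany the any-drug variable and not replace it.
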